### 11.1.7 Severe Hypoglycemia

Subject self-monitoring of blood glucose will be performed according to the standard of care as indicated by the investigator. This may include clinician-prescribed glucose monitoring devices, ie, glucose meters or continuous glucose monitoring devices (CGM). The number of severe hypoglycemic events will be collected as part of each study visit. Events are defined according to American Diabetes Association recommended criteria.

- Severe hypoglycemia denotes severe cognitive impairment requiring external assistance for recovery. Severe hypoglycemia is an event requiring assistance of another person to actively administer carbohydrates, glucagon, or take other corrective actions. Plasma glucose concentrations may not be available during an event, but neurological recovery following the return of plasma glucose to normal is considered sufficient evidence that the event was induced by a low plasma glucose concentration.
- In addition to the above criterion, for subjects using CGM, readings below the  $<54$  mg/dL (3.0 mmol/L) for at least 15 minutes will be considered severe hypoglycemia

Note that non-severe hypoglycemic events will not be collected or recorded in the study database, but that the investigator will monitor those types of events according to the site's standard of care.

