## 5.7 Study Endpoints

Consistent with the study objectives, the primary endpoints will focus on the safety and tolerability of AVT001 treatment versus placebo.

The primary endpoints are:

- (a) The incidence of treatment-emergent adverse events (TEAEs).
- (b) Changes from baseline in clinical laboratory parameters.
- (c) The incidence and severity of local IV-site reactions.
- (d) Changes from baseline in vital signs and electrocardiograms.
- (e) Incidence of severe hypoglycemic events.

Secondary objectives focus on the CD8+ T-cell regulatory system and therapeutic outcomes associated with T1D. These pharmacodynamic effects of AVT001 will be assessed in an exploratory manner.

Secondary endpoints will include:

- (a) Assessment of the HLA-E-restricted CD8+ T cell regulatory activity (“potency assay”)
- (b) Changes from baseline in the area under the curve (AUC) of the stimulated C-peptide levels over the first 4 hours of a mixed meal tolerance test (MMTT)
- (c) Changes from baseline in HbA1c
- (d) Change from baseline in total daily insulin dose
- (e) Changes from baseline in autoantibody levels

The primary time point for analysis is Month 5, at which point the primary assessment of the study objectives is performed.

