## 12. DISEASE HISTORY

The following disease history characteristics will be summarized overall and by treatment group based on the SAF analysis population:

- Time since diagnosis (days) – calculated relative to date of first infusion of study drug
- Use of insulin pump (yes/no)
- HbA1c at diagnosis, screening, and baseline (%)
- Change and percent change in HbA1c from diagnosis to baseline (%)
- Weight at diagnosis, screening, and baseline (kg)
- Change and percent change in weight from diagnosis to baseline (kg)
- BMI at diagnosis, screening, and baseline (kg/m^2)

Author:	[name]	Version Number:	2.0
Template No.:	CS_TP_BS016 Revision 6	Version Date:	23Nov2022
Effective Date:	02Dec2019	Reference:	CS_WI_BS005

- Change and percent change in BMI from diagnosis to baseline (kg/m^2)

All disease history characteristics will be listed.

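### Primary endpoint (e) pools assisted hypoglycemia with sensor lows that count only in CGM wearers, so its incidence depends on device use that the plan neither assigns nor reports

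*Combined protocol and SAP*

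**What the plan says.** Protocol Amendment 3, section 5.7, lists as primary endpoint (e): "Incidence of severe hypoglycemic events". Section 11.1.7 defines the event by two routes.

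- **All subjects:** "Severe hypoglycemia is an event requiring assistance of another person to actively administer carbohydrates, glucagon, or take other corrective actions".
- **CGM wearers only:** "In addition to the above criterion, for subjects using CGM, readings below the" level of 54 mg/dL "for at least 15 minutes will be considered severe hypoglycemia". No symptom or assistance is required.

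The trial does not assign the device: "Subject self-monitoring of blood glucose will be performed according to the standard of care as indicated by the investigator". The section allows either a meter or a CGM. It closes with: "Note that non-severe hypoglycemic events will not be collected or recorded in the study database".

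Section 9.6 tabulates severe events as one subject incidence and one number of events per subject, without separating the routes. Section 8.2.2 randomises 2:1 in blocks and names no stratification factor. Table 3 schedules a severe-hypoglycemia assessment at every visit from Day 1 but no CGM item.

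SAP v2.0, section 12, summarises insulin pump use but not CGM use, and section 7.7 plans no subgroups. Section 17.1.5 defines severe hypoglycemic events as adverse events coded to the Hypoglycaemia preferred term. It promises a listing, leaves a summary table optional, and cites neither section 11.1.7 nor CGM. SAP v1.0 reads the same on this point.

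**The concern.** Take the same unassisted low, below 54 mg/dL for 20 minutes, in two subjects. In a CGM wearer it is a primary-endpoint event. In a meter user it is neither an event nor recorded anywhere in the database, so it cannot be recovered later. A subject who starts CGM during follow-up becomes eligible for the second route only from then on.

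The pooled figure therefore mixes a clinical event that can be ascertained in everyone with a sensor finding that can be ascertained only in some, and neither document says how many. In a trial whose primary purpose is safety, planned at 16 against 8 subjects and reported descriptively, the definition carries most of the weight. A reader shown one incidence per arm could not tell whether it describes assisted events, sensor lows or the spread of CGM use.

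The SAP adds a second difficulty. Under section 17.1.5, a CGM-only low appears only if it was entered as an adverse event and coded to that one term. What is displayed may then match neither route in section 11.1.7.

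**Working it through.** **The plan's own figures.** The sample-size statement (protocol 9.2, SAP 7.1) reproduces: 1 − 0.88^14 = 0.833, which meets the stated 80%. Also 21/0.9 = 23.3, rounded up to 24. Neither figure concerns hypoglycemia and neither is disputed. The documents give no CGM share, assisted-event rate or sensor-low rate, so every rate below is an assumption, shown as a range.

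**Step 1: how the pooled incidence depends on device use.** Let r0 be the incidence without CGM, r1 the incidence by either route in CGM wearers, and c the CGM share. With no drug effect, pooled incidence = r0 + (r1 − r0)·c. Take r0 = 5%.

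| r1 | c = 0 | c = 50% | c = 100% |
|---|---|---|---|
| 30% | 5% | 17.5% | 30% |
| 50% | 5% | 27.5% | 50% |
| 80% | 5% | 42.5% | 80% |

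**Step 2: how large r1 might be.** If a wearer has one qualifying sensor low every w weeks at a constant rate, the chance of at least one by Day 150 is 1 − exp(−150/(7w)).

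- w = 5: 0.986
- w = 10: 0.883
- w = 20: 0.657
- w = 50: 0.35
- w = 100: 0.19

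The strength of the dependence is thus set by an unknown rate.

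**Step 3: chance imbalance in CGM use.** With K wearers among 24 subjects, the number x in the AVT001 arm of 16 is hypergeometric if CGM use is unrelated to order of entry. The difference in CGM share is x/16 − (K − x)/8. The probability of an absolute difference of 25 points or more is:

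- K = 6 or 18: 0.129
- K = 12: 0.193. The difference moves in steps of 3/16 = 18.75 points, so this is also the probability of 37.5 points or more.
- K = 8 or 16: 0.363, but this includes a tie at exactly 25 points. Beyond 25 points it is 0.19.
- K = 23: 0

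**Step 4: what such an imbalance would do.** With CGM use of 75% against 50% and no drug effect, the expected arm difference is 0.25·(r1 − r0).

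- r1 = 30%: 0.25 × 0.25 = 6.3 points
- r1 = 50%: 0.25 × 0.45 = 11.3 points
- r1 = 80%: 0.25 × 0.75 = 18.8 points

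**The case against.** A reader might infer that arm differences in this endpoint would reflect CGM wear rather than AVT001. The documents do not support that. Allocation is randomised (protocol 8.2.2) and Table 3 marks Visits 3 to 7 as double-blind, so device use at entry is not systematically tied to arm. Safety endpoints are not tested (SAP 7.4), so no false-positive decision follows. What remains is an absolute incidence that is hard to interpret, plus possible chance imbalance.

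A reader might also infer that assisted events would be lost among sensor lows. That is not shown. With about 24 subjects, SAP 17.1.5 commits to listing every event, adverse events are graded by CTCAE, and serious events are tabulated and listed separately. Many assisted events could probably be picked out, although no stated field marks which criterion was met.

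Nor can it be said that incidence simply tracks CGM use. That needs frequent sensor lows; at one per 50 or 100 weeks the link is much weaker. If nearly all subjects or none wear a CGM, imbalance between arms largely disappears.

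The assistance route still applies to everyone, and the CGM route only adds to it. The eCRF and table shells are not among the documents, so CGM use may already be captured there, but neither protocol nor SAP says so.

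These points limit the consequence. They do not remove the asymmetry in section 11.1.7, the pooling in section 9.6 or the mismatch with SAP 17.1.5.

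**Conclusion.** The point holds as a cheap improvement to the definition and reporting of one of five descriptive primary safety endpoints. As written, the pooled incidence depends on CGM use, which the plan does not assign, stratify or summarise, and the uncollected non-severe lows prevent a later repair. Differences between arms could partly reflect chance imbalance in CGM use at 16:8, in no particular direction.

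The size is unknown. The illustrations span from modest to large, and all rest on assumed CGM shares and event rates. The textual findings do not rest on those assumptions: two routes with different ascertainment are pooled in the protocol, and the SAP uses a third definition that refers to neither. No stated sample-size figure is wrong, and no view is taken on the clinical glucose threshold.

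**What to change.** Reconcile protocol sections 11.1.7 and 9.6 with SAP section 17.1.5. Editing the protocol alone would leave the SAP's coding-based output unchanged. SAP v2.0, section 4.4, says the plan will be amended before the final-analysis lock, and that amendment can specify:

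- events requiring another person's assistance, tabulated in all subjects as one outcome;
- CGM-only events (below 54 mg/dL for 15 minutes or more, unassisted) as a separate outcome, with CGM wearers as the denominator;
- a flag on each event for the criterion met;
- CGM use summarised by arm, recorded at the remaining visits and retrieved from source records for earlier ones.

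This is close to the sponsor's 2013 protocol (section 2.5), which listed major events, including those needing assistance, separately from glucose-confirmed lows.

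The cost is two data fields, one extra table, some retrieval from source records and a smaller headline count. The split would also be specified after unblinding: SAP v2.0, section 4.2, records that the Month 5 data were locked on 29 April 2022, except the potency assay, and unblinded on 17 May 2022. The report should disclose this.

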### 11.2 Recording of Adverse Events

At each contact with the subject, the investigator must seek information on adverse events by specific questioning and, as appropriate, by examination. Information on all adverse events should be recorded immediately in the source document, and also in the appropriate adverse event module of the case report form (CRF). All clearly related signs, symptoms, and abnormal diagnostic procedures results should be recorded in the source document, though should be grouped under one diagnosis.

All adverse events occurring during the study period must be recorded. The clinical course of each event should be followed until resolution, stabilization, or until it has been determined that the study treatment or participation is not the cause. Serious adverse events that are still ongoing at the end of the study period must be followed up to determine the final outcome. Any serious adverse event that occurs after the study period and is considered to be possibly related to the study treatment or study participation should be recorded and reported immediately.

### 11.3 Reporting of Adverse Events

#### 11.3.1 Adverse Event Reporting Period

The study period during which adverse events must be reported is defined as the period from the time of consent through the end of study or early termination, whichever is sooner. Reporting of Serious Adverse Events – Study Sponsor Notification by Investigator

A serious adverse event must be reported to the study sponsor by telephone within 24 hours of the event. A Serious Adverse Event (SAE) form must be completed by the investigator and faxed to the study sponsor within 24 hours. The investigator will keep a copy of this SAE form on file at the study site. Report serious adverse events by phone, facsimile or email to:

Name: [name], MD

Address: Iqvia Biotech, [name]

[contact] (US Toll-free: [name])

At the time of the initial report, provide as much of the following information as possible:

- Study identifier
- Study Center
- Subject number
- A description of the event
- Date of onset
- Current status
- Whether study treatment was discontinued
- The reason why the event is classified as serious
- Investigator assessment of the association and expectedness between the event and study treatment
- If the treatment blind was broken.

Within the following 48 hours, the investigator must provide further information on the serious adverse event in the form of a written narrative. This should include a copy of the completed Serious Adverse Event form, and any other diagnostic information that will assist the understanding of the event. Significant new information on ongoing serious adverse events should be provided promptly to the study sponsor.

### 11.3.2 IRB Notification

Each site's local policy for IRB reporting should be followed. All serious adverse events (SAEs) should be submitted to the Institutional Review Board/Independent Ethics Committee (IRB/IEC) within the timing of the local authority. The investigator should make an effort to obtain all hospital medical records including discharge summary confirming final diagnosis.

The death of a subject must be immediately (within 24 hours) reported to the IRB. Other Reportable Events

For clinical drug trials, the following events are also reportable to the IRB:

- Any adverse experience that, even without detailed analysis, represents a serious unexpected adverse event that is rare in the absence of drug exposure (such as agranulocytosis, hepatic necrosis, Stevens-Johnson syndrome).
- Any adverse event that would cause the sponsor to modify the investigators brochure, protocol or informed consent form, or would prompt other action by the IRB to assure protection of human subjects.
- Information that indicates a change to the risks or potential benefits of the research, in terms of severity or frequency. For example:
  - An interim analysis indicates that participants have a lower rate of response to treatment than initially expected.
  - Safety monitoring indicates that a particular side effect is more severe, or more frequent than initially expected.

- A paper is published from another study that shows that an arm of your research study is of no therapeutic value.
- Change in FDA safety labeling or withdrawal from marketing of a drug, device, or biologic used in a research protocol.
- Breach of confidentiality
- Change to the protocol taken without prior IRB review to eliminate apparent immediate hazard to a research participant.
- Incarceration of a participant when the research was not previously approved under Subpart C and the investigator believes it is in the best interest of the subject to remain on the study.
- Complaint of a participant when the complaint indicates unexpected risks or the complaint cannot be resolved by the research team.
- Protocol violation (meaning an accidental or unintentional deviation from the IRB approved protocol) that in the opinion of the investigator placed one or more participants at increased risk, or affects the rights or welfare of subjects.

### 11.3.3 FDA Notification by Sponsor

The study sponsor is required to report certain study events in an expedited fashion to the FDA. These written notifications of adverse events are referred to as IND safety reports. The following describes the safety reporting requirements by timeline for reporting and associated type of event:

- Within 7 calendar days

Any study event that is:

1. associated with the use of the study drug
2. unexpected,
3. fatal or life-threatening, and

- Within 15 calendar days

Any study event that is:

- associated with the use of the study drug,
- unexpected, and
- serious, but not fatal or life-threatening

-or-

- a previous adverse event that was not initially deemed reportable but is later found to fit the criteria for reporting (reporting within 15 calendar days from when event was deemed reportable).

Any finding from tests in laboratory animals that:

- suggest a significant risk for human subjects including reports of mutagenicity, teratogenicity, or carcinogenicity.

Sponsors are also required to identify in IND safety reports all previous reports concerning similar adverse events and to analyze the significance of the current event in light of the previous reports.

#### 11.4 Protocol Deviations

The investigator will maintain a protocol deviation log, in accordance with the site's local policy for IRB reporting, that describes departures from the study protocol. If the impact on the protocol disrupts the study design, may affect the outcome (endpoints) or compromises the safety and welfare of the subjects, the deviation will be reported to the Sponsor (and the IRB in accordance with the site's local policy) within 10 business days.

Any departure from the protocol that meets the following criteria should be submitted to the Sponsor:

- May/can/have affects/affected subject safety
- Violate eligibility
- Dose adjustment
- Stopping criteria
- Affect sample size (adding more subjects, decreasing number of subjects, changing the number of subject in a specific arm/cohort)

#### 11.5 Medical Monitoring

It is the responsibility of the Principal Investigators to oversee the safety of the study at their sites. This safety monitoring will include careful assessment and appropriate reporting of adverse events as noted above, as well as the construction and implementation of a site data and safety-monitoring plan. The Sponsor will be responsible for performing overall medical monitoring, including regular assessment of safety outcomes (e.g., review of laboratory data, review of adverse events and local tolerability outcomes across the sites).

## 12 Data Handling and Record Keeping

### 12.1 Confidentiality

Information about study subjects will be kept confidential and managed according to the requirements of the Health Insurance Portability and Accountability Act (HIPAA). Those regulations require a signed subject authorization informing the subject of the following:

- What protected health information (PHI) will be collected from subjects in this study
- Who will have access to that information and why
- Who will use or disclose that information
- The rights of a research subject to revoke their authorization for use of their PHI.

In the event that a subject revokes authorization to collect or use PHI, the investigator, by regulation, retains the ability to use all information collected prior to the revocation of subject authorization. For subjects that have revoked authorization to collect or use PHI, attempts should be made to obtain permission to collect at least vital status (i.e. that the subject is alive) at the end of their scheduled study period.

### 12.2 Source Documents

Source data is all information, original records of clinical findings, observations, or other activities in a clinical trial necessary for the reconstruction and evaluation of the trial. Source data are contained in source documents Examples of these original documents, and data records include: hospital records, clinical and office charts, laboratory notes, memoranda, subjects' diaries or evaluation checklists, pharmacy dispensing records, recorded data from automated instruments, copies or transcriptions certified after verification as being accurate and complete, microfiches, photographic negatives, microfilm or magnetic media, x-rays, subject files, and records kept at the pharmacy, at the laboratories, and at medico-technical departments involved in the clinical trial.

### 12.3 Case Report Forms

Clinical study data will be captured / collected in a clinical study database using electronic case report forms (eCRFs) in a CFR Title 21 part 11-compliant system. All data requested in the eCRF must be recorded, and reasons for missing data should be provided.

### 12.4 Records Retention

It is the investigator's responsibility to retain study essential documents according to regulatory requirements. These documents may be retained for a longer period if required by an agreement with the sponsor. In such an instance, it is the responsibility of the sponsor to inform the investigator/institution as to when these documents no longer need to be retained.

## 13 Study Monitoring, Auditing, and Inspecting

### 13.1 Study Monitoring Plan

This study will be monitored according to the study monitoring plan. The investigator will allocate adequate time for such monitoring activities. The Investigator will also ensure that the monitor or other compliance or quality assurance reviewer is given access to all the above noted study-related documents and study related facilities (e.g. pharmacy, diagnostic laboratory, etc.), and has adequate space to conduct the monitoring visit.

### 13.2 Auditing and Inspecting

The investigator will permit study-related monitoring, audits, and inspections by the EC/IRB, the sponsor, government regulatory bodies, and University compliance and quality assurance groups of all study related documents (e.g. source documents, regulatory documents, data collection instruments, study data etc.). The investigator will ensure the capability for inspections of applicable study-related facilities (e.g. pharmacy, diagnostic laboratory, etc.).

Participation as an investigator in this study implies acceptance of potential inspection by government regulatory authorities and applicable University compliance and quality assurance offices.

## 14 Ethical Considerations

This study is to be conducted according to US and international standards of Good Clinical Practice (FDA Title 21 part 312 and International Conference on Harmonization guidelines), applicable government regulations and Institutional research policies and procedures.

This protocol and any amendments will be submitted to a properly constituted independent Ethics Committee (EC) or Institutional Review Board (IRB), in agreement with local legal prescriptions, for formal approval of the study conduct. The decision of the EC/IRB concerning the conduct of the study will be made in writing to the investigator and a copy of this decision will be provided to the sponsor before commencement of this study. The investigator should provide a list of EC/IRB members and their affiliate to the sponsor.

All subjects for this study will be provided a consent form describing this study and providing sufficient information for subjects to make an informed decision about their participation in this study. This consent form will be submitted with the protocol for review and approval by the EC/IRB for the study. The formal consent of a subject, using the EC/IRB-approved consent form, must be obtained before that subject is submitted to any study procedure. This consent form must be signed by the subject or legally acceptable surrogate, and the investigator-designated research professional obtaining the consent.

